7.6 Safety

The safety analyses will be based on the all treated population defined in Section 6. Adverse events are graded and categorized using the NCI CTCAE.

7.6.1 Adverse Events and Serious Adverse Events

Adverse Events (AEs) sections of CRF Surgery REPORT, CRF FOLLOW UP REPORT and CRF SHORT FOLLOW UP REPORT record ongoing or new AEs related (possibly, probably, or definitely) to surgery observed respectively within 4 weeks of surgery, during follow-up but before the first pelvic relapse, and after the first pelvic relapse. AEs reported on CRF SURGERY REPORT are defined as acute AEs and those reported on CRF FOLLOW UP REPORT and CRF SHORT FOLLOW UP REPORT as late AEs. Severe adverse events are those events reported with a CTCAE Grade of 3 or higher.

The following variables are summarized:

- Acute adverse events: worst CTCAE grade per patient (**Table 32**)
- Severe acute adverse events: worst CTCAE grade per patient (**Table 33**)
- Late adverse events: worst CTCAE grade per patient (**Table 34**)
- Severe late adverse events: worst CTCAE grade per patient (**Table 35**)

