2.2 Management of Patients with Low-risk Cervical Cancer

For over a century, radical hysterectomy with pelvic lymphadenectomy has been the standard surgical approach for patients with stage IA2- IB1 disease. Various rates of important acute morbidities have been reported following radical hysterectomy, with differences likely reflecting the rigor of assessment. Complications include urinary and rectal dysfunction, ureteral and vesical fistulas (2%), intraoperative bleeding, infections and lymphedema [Sood 2002]. Urinary dysfunction includes difficulty voiding, postoperative urinary retention and loss of urinary sensation. According to Ceballos, overall morbidity of radical hysterectomy reaches 10%, with a 2% risk of ureteric injury and a 7% risk of lymphedema [Ceballos 2006]. Matsuura reported that complete pelvic lymph node dissection is associated with up to a 20% risk of lymphocyst formation, 10-15% risk of lymphedema, and rare cases of neural or vascular damage [Matsuura 2006]. Others report severe perioperative complications in 10-15% of cases [Averette 1993; Benedetti-Panici 2005]. Urological and rectal dysfunction related to nerve injury has been reported in up to 20-30% of cases [Averette 1993; Benedetti-Panici 2005]. Sood evaluated the incidence of bowel symptoms, changes in anorectal physiology and quality of life after radical hysterectomy and concluded that bowel dysfunction is common and due to pudendal neuropathy, autonomic dysfunction or both [Sood 2002; Sartori 1997].

Late complications are also important. Even though sensory and motor bladder dysfunction affect a majority of women in the immediate postoperative period, and may be a function of the extent of the operation, 1-2% will have long-term detrusor dysfunction or markedly decreased sensory function leading to inferior scores in assessments of quality of life [Sood 2002]. Late complications can also include hydronephrosis and lymphedema in up to 16% of cases [Magrina 1995].

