
 1. This visit may be done up to 6 weeks after surgery. 2. A recto-vaginal examination is preferred but not mandatory. A bimanual exam is also acceptable. 3. Adverse events will be recorded and graded according to the NCI Common Terminology Criteria for Adverse Events (CTCAE) Version 4.0 (Appendix V). Only AEs deemed possibly, probably, or definitely related to protocol therapy need to be reported. 4. For patients who consented to this optional study component and/or select GCIG groups . 5. Mandatory for English and French speaking patients from Canada, the UK and select GCIG groups. 		

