APPENDIX IV - DOCUMENTATION FOR STUDY

Follow-up is required for patients from the time of randomization and will apply to all eligible patients.

This trial will use a web-based Electronic Data Capture (EDC) system for all data collection except the quality of life questionnaire, sexual health questionnaire and the health economics questionnaire. For details of accessing the EDC system and completing the on-line Case Report Forms please refer to the “CCTG EDC Generic Data Management Guidebook” posted on the CX.5 area of the CCTG web-site (www.ctg.queensu.ca).

The electronic CRFs to be used in this trial, through the EDC system, are as follows:

Electronic Folder	Required	To be completed electronically	De-Identified Supporting Documentation Required ¹
Eligibility Checklist	Prior to randomization	At the time of randomization	
Baseline Report	Prior to protocol surgery	Within 6 weeks after randomization	
 • Consent form signature pages (Canadian patients only) • Copies of pathology reports (from initial diagnosis and LRP review) and radiology reports² • PROs³
LEEP/cone/biopsy Checklist			
Surgery Report	4-6 weeks after protocol surgery	Within 8 weeks after surgery	
 • Operative report • Pathology report • Photograph of hysterectomy specimen for surgical QA⁴ • Lymphocintogram and photographs for SN mapping QA⁵
Adjuvant Therapy Report	Upon the completion of adjuvant therapy	Within 8 weeks after the completion of adjuvant therapy	--
Follow-Up Report	Year One – q 3 monthly ⁶ Year Two – q 4 monthly Year Three – q 6 monthly Then q 12 months until study closure. ⁷	Within 8 weeks of the visit date	
 • Pelvic exam notes • Radiology reports (if done) • Pathology/cytology/surgical reports (if done) • PROs³
Recurrence Report	At the time of first pelvic and/or extra-pelvic disease recurrence	Within 8 weeks of the date of recurrence	
 • Pelvic exam notes • Radiology reports (if done) • Pathology/cytology/surgical reports (if done) • PROs³
Short Follow-up Report	q 6 monthly from the date of the most recent recurrence	Within 8 weeks of the visit date	
 • Pelvic exam notes (if done) • Radiology reports (if done) • Pathology/cytology/surgical reports (if done)
Death Report	At the time of patient death	Within 8 weeks of patient death	Autopsy report (if done)

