SAE Report ⁸	At the time of the event	See section 11.0	

 1. Supporting Documentation should be uploaded into the EDC system Supporting Document Upload Tool after the eCRF has been submitted electronically. 2. Original diagnostic specimen and/or MRI images may be requested for central review purposes (see Section 13). 3. Patient Reported Outcomes (QoL, Sexual Health, Health Economics) for applicable patients should be uploaded into the EDC system Supporting Document Upload Tool after the eCRF has been submitted electronically. 4. See Section 13 and the Surgery/Pathology manual for full details. 5. For sites performing SN mapping (see Section 13 and the Surgery/Pathology manual). 6. The reporting period for the first Follow-Up Report will start from the date of the 4-6 week post-surgery visit and collect data up until the date of the first follow-up visit. 7. Calculated from the date of protocol surgery. 8. See section 11.0 Serious Adverse Event Reporting for details. 			

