7.6.2 Other Safety

- Any pelvic exam after 4 weeks of surgical treatment but before the first pelvic recurrence (reported on CRF Follow-up Report): yes, no (**Table 36**)
- Results of pelvic exams after 4 weeks of surgical treatment but before the first pelvic recurrence (reported on CRF Follow-up Report): all normal, at least one abnormal but all non-malignant, all abnormal and malignant (**Table 36**)

- Any pelvic exam after the first pelvic recurrence (reported on CRF Follow-up Report): yes, no (**Table 36**)
- Results of pelvic exams after the first pelvic recurrence (reported on CRF Short Follow-up Report): all normal, at least one abnormal but all non-malignant, all abnormal and malignant (**Table 36**)
- Any other radiologic investigations within 4 weeks of surgical treatment (reported on CRF Surgery Report): yes, no (**Table 37**)
- Results of other radiologic investigations within 4 weeks of surgical treatment by site and method of investigations: all normal, at least one abnormal but all non-malignant, all abnormal and malignant (**Table 37**)
- Any other radiologic investigations after 4 weeks of surgical treatment but before the first pelvic recurrence (reported on CRF Follow-up Report): yes, no (**Table 37**)
- Results of other radiologic investigations after 4 weeks of surgical treatment but before the first pelvic recurrence (reported on CRF Follow-up Report): all normal, at least one abnormal but all non-malignant, all abnormal and malignant (**Table 37**)
- Any other radiologic investigations after the first pelvic recurrence (reported on CRF Follow-up Report): yes, no (**Table 37**)
- Results of other radiologic investigations after the first pelvic recurrence (reported on CRF Short Follow-up Report): all normal, at least one abnormal but all non-malignant, all abnormal and malignant (**Table 37**)
- Any hospitalization after 4 weeks of surgical treatment but before the first pelvic recurrence (reported on CRF Follow-up Report): yes, no (**Table 38**)
- Any hospitalization after the first pelvic recurrence (reported on CRF Follow-up Report): yes, no (**Table 38**)

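### Late adverse events are defined by reporting form, with no onset or persistence rule, so Tables 34-35 cannot tell slow post-operative recovery from lasting morbidity

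*SAP*

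**What the plan says.** SAP 7.6.1 states that the adverse event sections of the Surgery Report, Follow Up Report and Short Follow Up Report "record ongoing or new AEs related (possibly, probably, or definitely) to surgery observed respectively within 4 weeks of surgery", then during follow-up before the first pelvic relapse, and then after it. The classification follows the form: "AEs reported on CRF SURGERY REPORT are defined as acute AEs and those reported on CRF FOLLOW UP REPORT" and on the Short Follow Up Report are late. The summary for Table 34 is "Late adverse events: worst CTCAE grade per patient", and Table 35 does the same for grade 3 or higher. No onset date, duration or assessment time enters either table.

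The protocol sets the form timing. In Appendix IV the Surgery Report is required "4-6 weeks after protocol surgery", and note 6 says "The reporting period for the first Follow-Up Report will start from the date of the 4-6 week post-surgery visit". Protocol 9.1 labels that visit week 4 but adds "This visit may be done up to 6 weeks after surgery".

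For hospital admissions, Table 17 covers the admission for the hysterectomy. The first hospitalization row planned for Table 38 (SAP 7.6.2) is "Any hospitalization after 4 weeks of surgical treatment but before the first pelvic recurrence (reported on CRF Follow-up Report".

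**The concern.** Protocol 2.1 gives fewer late effects as part of the reason for testing the smaller operation, and treatment-related adverse events are a named secondary endpoint. Protocol 2.2 separates two kinds of bladder problem after radical surgery: most women are affected in the immediate post-operative period, but "1-2% will have long-term detrusor dysfunction" or markedly reduced sensation. A late-toxicity table should be able to separate these two.

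Tables 34-35 cannot. An event that began in the first days after surgery and is still noted on the first Follow-Up Report is late, and it may also be counted as acute. One that clears at month 4 has the same weight as one present at month 36. If transient problems resolve more slowly after one operation, the late tables can show a difference between arms with no difference in lasting harm. Using the same rule in both arms does not remove this.

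The boundary itself is also unsettled, because the SAP's 4 weeks and Appendix IV's 4-6 week visit are not the same date.

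**Working it through.** The plan gives no rate, power or sample size for acute or late events, so there is no figure to reproduce. The check sets the windows side by side and then asks how large the mixing could be.

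**Windows.** Inputs: the acute window ends at week 4 (SAP 7.6.1); the first Follow-Up Report starts at the visit, weeks 4 to 6 (Protocol 9.1 and Appendix IV note 6); the next visit is at week 12 (Protocol 9.1).

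- Days uncovered on the SAP's literal wording = (visit week - 4) x 7.
- Weeks before the week-12 visit that are classed as late = 12 - visit week.

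| Visit week | Days uncovered | Late weeks before week 12 |
|---|---|---|
| 4 | 0 | 8 |
| 5 | 7 | 7 |
| 6 | 14 | 6 |

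If the Surgery Report in fact runs to the visit, nothing is uncovered. A week-5 event is then late for a woman seen at week 4 and acute for one seen at week 6. Neither document says which reading applies. Under both, 6 to 8 weeks of early recovery fall in the late category.

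**Possible size of the mixing (bladder dysfunction, illustration only).** Inputs: 50% stands for the majority affected early (Protocol 2.2); L is the long-term rate, 1-2% (Protocol 2.2); f is the share of early cases still present after the 4-6 week visit. The documents do not give f, so it is assumed.

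Rate in the late table = 0.5 x f. Transient share of that rate = 1 - L / (0.5 x f), set to 0 where the late-table rate does not exceed L.

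| f (assumed) | Late-table rate | Transient share, L = 1% | Transient share, L = 2% |
|---|---|---|---|
| 2% | 1% | 0% | 0% |
| 5% | 2.5% | 60% | 20% |
| 10% | 5% | 80% | 60% |
| 20% | 10% | 90% | 80% |

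L is not fixed either. A study cited in Protocol 2.2 found 11% long-term bladder dysfunction after modified radical hysterectomy, the term Protocol 13.3.1 uses for the Arm 1 specimen. With L = 11%, the transient share stays at 0% until f exceeds 0.11 / 0.5 = 22%. In the planned 350 women per arm, 1-2% is 3.5 to 7 women and 11% is 38.5.

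**Early readmissions.** Table 17 stops at discharge from the index admission, and Table 38 starts after week 4. Table 37 (radiology) and Table 23 (procedures) do have rows for the first 4 weeks. A readmission before week 4 that is managed without a procedure has no row of its own.

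**The case against.** The strongest reply is that the trial's main test of lasting bladder and bowel effects lies elsewhere. Hypothesis 1 in Protocol 2.5.3 assigns it to the QLQ-CX24, collected at 3, 6, 12, 24 and 36 months, compared by arm at each time (SAP 7.8.4.1, Table 44) and modelled over time (SAP 7.8.4.2). This stands. A reader might infer that the plan as a whole cannot separate recovery from lasting dysfunction, and that would be wrong. The limit applies to the clinician-graded CTCAE tables, which the questionnaires complement but do not replace. The questionnaires also reach only women able to complete them in an available language.

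Second, the forms can be read as joining. The Surgery Report is due at 4-6 weeks, the first Follow-Up Report starts at that visit, and 4 weeks may be a nominal visit label. On that reading every reported event is classified, and what remains is a boundary that moves by at most two weeks. This is plausible, but it is not stated. A definite hole in data collection is not shown.

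Third, an event still present at three months can fairly be called late, Table 35 isolates the severe ones, and Tables 32-35 are descriptive, with no p-value column. All of this is true. But Protocol 14.2 still allows Fisher's exact tests between arms as needed, and persistence can be reported only if the table shows when the event was present.

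Fourth, early readmissions need not be lost. Hospitalization is a seriousness criterion (Protocol 11.1), serious events must be recorded on case report forms (Protocol 11.0), and related events appear in Tables 32-33. What is missing is a dedicated row.

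**Conclusion.** The definitional point holds and needs no assumed rate. Late status depends on the form alone, ongoing events carry over, and worst grade over all follow-up removes timing. Short-term post-operative events can therefore enter Tables 34-35 to an unknown extent and cannot be told apart there from lasting morbidity.

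A reader might go further and conclude that these tables would consist mainly of short-term events, by setting an assumed persistence against the 1-2% long-term figure. The documents do not support that. They give no persistence rate, the 11% figure points to a much higher long-term rate, and the illustration runs from no transient share to 90%.

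The window mismatch is real as text: 0 to 14 days uncovered on the literal wording, or a boundary differing by up to two weeks if the Surgery Report runs to the visit. This and the missing readmission row are secondary. The change is worth making before the safety tables are produced. The primary non-inferiority analysis is not affected.

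**What to change.** In SAP 7.6.1:

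- Reconcile the Surgery Report window with Appendix IV note 6, stating the period that the form actually captured.
- Set one boundary in days from surgery for all women. Count an event as late only if it is new after that boundary or still present at a stated later visit. Where onset is not recorded, classify by visit.
- State how an acute event that continues is shown in the acute and late tables.

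In the tables:

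- Add to Tables 34-35 the proportion with each surgical-morbidity term at the 12, 24 and 36 month visits, by arm.
- Add to Table 17 or 38 a row for readmission between discharge and the 4-6 week visit, where the case report forms or resource-utilization data capture it.

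The cost is SAP wording and a few table rows, since Protocol 9.1 already requires adverse events to be evaluated at every visit. Two limits remain. The documents do not show whether onset dates are recorded, and early-readmission data may be incomplete, particularly outside the countries in the economic study.

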7.6.2 Other Safety

- Any pelvic exam after 4 weeks of surgical treatment but before the first pelvic recurrence (reported on CRF Follow-up Report): yes, no (**Table 36**)
- Results of pelvic exams after 4 weeks of surgical treatment but before the first pelvic recurrence (reported on CRF Follow-up Report): all normal, at least one abnormal but all non-malignant, all abnormal and malignant (**Table 36**)

- Any pelvic exam after the first pelvic recurrence (reported on CRF Follow-up Report): yes, no (**Table 36**)
- Results of pelvic exams after the first pelvic recurrence (reported on CRF Short Follow-up Report): all normal, at least one abnormal but all non-malignant, all abnormal and malignant (**Table 36**)
- Any other radiologic investigations within 4 weeks of surgical treatment (reported on CRF Surgery Report): yes, no (**Table 37**)
- Results of other radiologic investigations within 4 weeks of surgical treatment by site and method of investigations: all normal, at least one abnormal but all non-malignant, all abnormal and malignant (**Table 37**)
- Any other radiologic investigations after 4 weeks of surgical treatment but before the first pelvic recurrence (reported on CRF Follow-up Report): yes, no (**Table 37**)
- Results of other radiologic investigations after 4 weeks of surgical treatment but before the first pelvic recurrence (reported on CRF Follow-up Report): all normal, at least one abnormal but all non-malignant, all abnormal and malignant (**Table 37**)
- Any other radiologic investigations after the first pelvic recurrence (reported on CRF Follow-up Report): yes, no (**Table 37**)
- Results of other radiologic investigations after the first pelvic recurrence (reported on CRF Short Follow-up Report): all normal, at least one abnormal but all non-malignant, all abnormal and malignant (**Table 37**)
- Any hospitalization after 4 weeks of surgical treatment but before the first pelvic recurrence (reported on CRF Follow-up Report): yes, no (**Table 38**)
- Any hospitalization after the first pelvic recurrence (reported on CRF Follow-up Report): yes, no (**Table 38**)

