9.1 Evaluation After Completion of Protocol Therapy

The information below is captured using the Follow-Up Report.

Investigations		Timing from the End of Treatment until first disease recurrence or study closure (see definition in Section 9.0)
Physical Exam including:	
 • performance status • weight • tobacco smoking status 	Year One – 4 ¹ and 12 weeks then q 3 monthly Year Two – q 4 monthly Year Three – q 6 monthly Then q 12 months.
Pelvic exam	
 • recto-vaginal examination with speculum or colposcopy² 	Year One – q 3 monthly Year Two – q 4 monthly Year Three – q 6 monthly Then q 12 months.
Radiology	
 • CT scan of abdomen and pelvis • chest radiograph 	As clinically indicated
Adverse Events ³	
 • Patients must be evaluated for related adverse events at each follow-up visit. 	Year One – 4 ¹ and 12 weeks then q 3 monthly Year Two – q 4 monthly Year Three – q 6 monthly Then q 12 months.
Resource Utilization Assessment (RUA)	
 • Supportive care medications, laboratory tests, imaging studies, radiotherapy, transfusions, hospitalization, and outpatient care, including physician, emergency room and home care visits⁴. 	Year One – 4 ¹ and 12 weeks then q 3 monthly Year Two – q 4 monthly Year Three – q 6 monthly Then q 12 months.
Patient Reported Outcomes	
 • Quality of Life questionnaire (composed of the QLQ-C30, QLQ-CX24) • Sexual Health questionnaire (composed of the FSDS-R and the FSFI)⁴ 	At 3 months, 6 months, 12 months, 24 months, 36 months and at first disease recurrence (if applicable).
	
 • Health Economics questionnaire (composed of the HUI3 and EQ-5D)⁵ 	Year One – 4 ¹ and 12 weeks then q 3 monthly Year Two – q 4 monthly Year Three – q 6 monthly Then q 12 months until study closure and at first disease recurrence (if applicable).

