9.2 Evaluation After Recurrence

Investigations Evaluations after pelvic and/or extra pelvic recurrence		Timing from the date of first recurrence (see Section10.3)
Physical Exam including:	
 • performance status • weight • tobacco smoking status 	At the time of first recurrence* AND Years One to Three – q 6 monthly Then q 12 months until study closure.
Pelvic Exam	
 • recto-vaginal examination with speculum or colposcopy** 	
Radiology	
 • CT or MRI scan of abdomen and pelvis • chest radiograph 	If clinically indicated
Adverse Events***	
 • Patients must be evaluated for related adverse events at each follow-up visit. 	Years One to Three – q 6 monthly Then q 12 months until study closure.

* A full “work-up” for pelvic recurrence is required at the time extra-pelvic recurrence is diagnosed. ** A recto-vaginal examination is preferred but not mandatory. A bimanual exam is also acceptable. *** Adverse events will be recorded and graded according to the NCI Common Terminology Criteria for Adverse Events (CTCAE) Version 4.0 (Appendix V). Only AEs deemed possibly, probably, or definitely related to protocol therapy need to be reported.
		

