7.7 Other Anti-Cancer Treatments and Tobacco Smoking History During Follow-up

Patients may receive surgical, systemic or radiation treatments for cervical cancer other than the protocol surgery and adjuvant treatments given 4 weeks within the protocol surgery treatment or smoke tobacco during the follow-up.

- Any surgery/procedure given 4 weeks after the surgery but before the first pelvic recurrence (reported on Follow Up Report) : yes, no (**Table 39**)
- Type and reason for surgery/procedure given 4 weeks after the surgery but before the first pelvic recurrence (reported on Follow Up Report) (**Table 39**)
- Any surgery/procedure given after the first pelvic recurrence (reported on Short Follow Up Report): yes, no (**Table 39**)
- Type and reason for surgery/procedure given after the first pelvic recurrence (reported on Short Follow Up Report) (**Table 39**)
- Any other anti-cancer treatment given 4 weeks after the surgery but before the first pelvic recurrence (reported on Follow Up Report): yes, no (**Table 40**)
- Type and treatment name or site for other anti-cancer treatment given 4 weeks after the surgery but before the first pelvic recurrence (reported on Follow Up Report) (**Table 40**)
- Any other anti-cancer treatment given after the first pelvic recurrence (reported on Short Follow Up Report): yes, no (**Table 40**)

- Type and treatment name or site for other anti-cancer treatment given after the first pelvic recurrence (reported on Short Follow Up Report) (**Table 40**)
- Smoked tobacco 4 weeks after the surgery but before the first pelvic recurrence (reported on Follow Up Report): yes, no (**Table 41**)
- Smoked tobacco after the first pelvic recurrence (reported on Short Follow Up Report): yes, no (**Table 41**)

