7.8.3 Compliance

Compliance with each PRO questionnaire will be described for each treatment arm, at each time of evaluation, by the number and percentage of expected subjects who filled

out a questionnaire (per subject, at least one question answered) in time of evaluation. The expected number used in calculating the percentage will be all alive subjects who are required to complete the assessment in each treatment arm at each assessment time point except at the first pelvic recurrence time point, which will be the number of alive patients who have the first pelvic recurrence (**Table 42**).

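### SAP 7.6.2 takes post-recurrence rows from a form the SAP itself confines to the pre-recurrence period, and SAP 7.6.2 to 7.8 split at first pelvic recurrence where the protocol splits at first recurrence of any site

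*SAP*

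**What the plan says.** **Forms.** SAP 7.6.1 assigns the Surgery Report to the first 4 weeks. It assigns the Follow Up Report and the Short Follow Up Report, respectively, to the periods "during follow-up but before the first pelvic relapse, and after the first pelvic relapse". For late adverse events it pools the two: "those reported on CRF FOLLOW UP REPORT and CRF SHORT FOLLOW UP REPORT as late AEs".

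**Source of the post-recurrence rows.** SAP 7.6.2 has the row "Any hospitalization after the first pelvic recurrence (reported on CRF Follow-up Report): yes, no". The yes/no rows for pelvic exam and for other radiology after first pelvic recurrence also cite the Follow-up Report. The results rows paired with those two cite the Short Follow-up Report. SAP 7.7 uses the short form for all its post-recurrence items, for example "Any other anti-cancer treatment given after the first pelvic recurrence (reported on Short Follow Up Report".

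**Boundary.** SAP 7.6.2 and 7.7 split at first pelvic recurrence. At the recurrence time point, SAP 7.8.3 sets the expected number of questionnaires as the one "which will be the number of alive patients who have the first pelvic recurrence". Protocol 9.1, captured on the Follow-Up Report, is headed "Timing from the End of Treatment until first disease recurrence or study closure". Protocol 9.2 is headed "Evaluations after pelvic and/or extra pelvic recurrence". Appendix I, footnote 8, makes the quality of life and sexual health questionnaires due at first disease recurrence, with no restriction on site.

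**Result categories.** SAP 7.6.2 classifies exam and radiology results as "all normal, at least one abnormal but all non-malignant, all abnormal and malignant". The shells of Tables 36 and 37 grade by clinical significance instead.

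**The concern.** These tables describe what happened to women before and after relapse: examinations, imaging, admissions, further surgery, systemic and radiation treatment, smoking and questionnaire completion. Three things can go wrong if the text is programmed literally.

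- A row asking what happened after recurrence may be filled from a form that, by the SAP's own account, is no longer in use by then.
- A woman whose first relapse is extra-pelvic has no clear place in a pelvic before/after split.
- A woman with a normal exam followed by a malignant one fits no result category.

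The trial's rationale is reduced morbidity at preserved disease control. A blank or short count of post-relapse admissions could be read as a finding when it is only a sourcing slip.

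**Working it through.** There is no stated figure to reproduce, so the check sets the texts side by side.

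**1. Source form.** Where does the Follow-Up Report end?

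| Text | Follow-Up Report runs until | Post-pelvic-recurrence row drawn from it |
|---|---|---|
| SAP 7.6.1 | first pelvic relapse | empty |
| Protocol 9.1 heading | first recurrence, any site | empty |
| Protocol Appendix IV row | study closure | could hold data |

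Only the third reading fills the row. It conflicts with 7.6.1, with the paired results rows and with 7.7. The shells of Tables 36 and 37 nest the results under a yes answer, so literal programming could put few or no yes patients above non-empty result rows.

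Hospitalization has no paired results row to reveal the slip. Protocol 9.1 lists it under resource utilization. Protocol 9.2 lists no such item, and Appendix I leaves resource utilization blank after recurrence.

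**2. Boundary.** Appendix I, footnote 3, attached to the after-recurrence column, requires pelvic exams in women whose first recurrence is extra-pelvic until a pelvic one is seen. The protocol therefore places women without pelvic recurrence on the post-recurrence schedule. Take such a woman and her later treatment in Table 40:

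- If rows are selected by form alone, her treatment appears as given after pelvic recurrence. She is misplaced.
- If both the event and the form in 7.7 are required, she fails the after row (no pelvic recurrence) and the before row (wrong form). She is omitted.
- If the forms really switch at first pelvic relapse, as 7.6.1 says, she stays in the before row. That is correct by its label, but her relapse treatment is mixed with pre-relapse care.

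**3. Questionnaires at recurrence.** They are due at first recurrence of any site; 7.8.3 counts pelvic recurrences only. Let P be women with a first pelvic recurrence and E those with a first extra-pelvic one. The share of women due a questionnaire but outside the denominator is E/(P+E).

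SAP 2.1 gives 14 pelvic recurrences at an interim date. E is not given. Taking P = 14, and assuming all were first recurrences in women alive and required to complete the form:

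| Assumed E | E/700 | E/(14+E) |
|---|---|---|
| 0 | 0% | 0% |
| 3 | 0.4% | 3/17 = 18% |
| 7 | 1.0% | 7/21 = 33% |
| 14 | 2.0% | 14/28 = 50% |

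This is an illustration, not an estimate.

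**4. Result categories.** Code each exam N (normal), B (abnormal, not malignant) or M (malignant). Two exams give 3 × 3 = 9 ordered sequences. The 7.6.2 text covers NN; NB, BN and BB; and MM, which is 5. It leaves NM, MN, BM and MB unclassified, which is 4 of 9. Normal exams followed by a malignant one, a natural course for a recurrence, fall in the gap.

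**The case against.** The strongest reply is that these are drafting slips in descriptive tables and that a programmer would notice them. Much of it stands. Tables 36 to 42 carry no p-value. SAP 7.8 itself also speaks of the first recurrence without naming a site, and the shells of Tables 42 and 44 say recurrence, not pelvic recurrence; the questionnaire text is inconsistent rather than uniformly pelvic. The shells of Tables 36 and 37 already use an exhaustive hierarchy, though on a different scale. An any-site form switch is well supported by protocol 9.1, 9.2 and Appendix I, but Appendix IV does not state it: its Short Follow-up row refers only to the most recent recurrence, and the case report forms are not in the documents.

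A reader might infer more than this. Four stronger readings are not supported.

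- *The safety tables as a whole are wrong.* Acute adverse events come from the Surgery Report and late ones pool both follow-up forms, so Tables 32 to 35 do not depend on the boundary.
- *Compliance at recurrence will exceed 100%.* SAP 7.8.3 reports a percentage of expected subjects, so the numerator lies within the denominator. Women with extra-pelvic first relapse are left out, not over-counted.
- *A third to a half of post-relapse women are mislabelled.* That needs a count the documents do not give, and selection by form with the recurrence condition ignored.
- *Admissions after relapse are known to be missed.* Nothing shows that they are collected after recurrence at all.

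What the reply does not remove is that SAP 7.6.2 contradicts 7.6.1 on the source form, and that the pelvic boundary and denominator disagree with the protocol.

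**Conclusion.** The point holds as a sourcing and definition defect confined to SAP 7.6.2 to 7.8 and Tables 36 to 42, with a wording consequence in 7.6.1. The three mis-sourced yes/no rows and the gap in the result categories can be shown from the SAP alone. The boundary mismatch rests on protocol 9.1, 9.2 and Appendix I, and on the assumption that the forms follow that schedule. It affects only women whose first relapse is extra-pelvic, probably few. The consequence is that some rows may be empty, short or misplaced if programmed literally, not that they certainly will be. The primary endpoint is taken from the Recurrence Report and is unaffected. The correction should be made before the tables are programmed, but it does not bear on the non-inferiority conclusion.

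**What to change.** 1. Use one boundary, first recurrence at any site, throughout SAP 7.6.2 to 7.8 and Tables 36 to 42, and align the wording of 7.6.1. Where a pelvic split is wanted, make it by date and site on the Recurrence Report.
2. Source the post-recurrence pelvic exam and radiology rows from the Short Follow-up Report.
3. Check whether that form has a hospitalization field. If so, cite it; if not, delete the row. Expedited serious adverse event reports are no substitute: under protocol 11.1 they cover only unexpected, treatment-related events and would miss admissions for the relapse itself.
4. In 7.8.3, set the denominator at recurrence to women alive with a first recurrence at any site who are required to complete the questionnaire.
5. Use one exhaustive scale in the 7.6.2 text and in the shells of Tables 36 and 37: any malignant; any abnormal but none malignant; all normal.

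The cost is edits to SAP text and table shells, plus one look at the form. No new data are needed.
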